4.1.2 Rehabilitation in Parkinson's Disease

The clinical management of PD has traditionally been centred on drug-based therapy (i.e. Levodopa) and surgical approaches (i.e., deep brain stimulation). Nonetheless, despite the undeniable usefulness of such treatments, PD patients still experience progressive motor deterioration and disability largely due to gait, balance and posture impairments (Abbruzzese et al., 2016).

A growing body of evidence highlights the effectiveness of physical therapy in PD and its positive effects on both motor and non-motor complications of PD (Abbruzzese et al., 2016; Tomlinson et al., 2013; van der Kolk and King, 2013). Due to these promising results and the amelioration of quality of

life, physiotherapy rehabilitation programs are currently considered an essential component of the management of patients with PD.

Importantly, rehabilitation was shown to have a positive effect on the risk of fall in a large metanalysis study (Shen et al., 2016), showing a significant overall fall rate reduction over both the short and long term, and supporting the application of exercise training to improve balance and gait ability and ultimately prevent falls in people with PD.

Although the evidence for a positive effect of physiotherapy rehabilitation treatments in PD is increasingly clear, some open questions remain to be further explored. One such question is which type of intervention yields the best results, and for how long the effect persists. Recent studies have shown that some forms of exercise such as balance training, gait training or complementary techniques such as Tai Chi can improve balance and mobility, as well as reduce fall frequency for up to six months after the end of training (Mak et al., 2017). This promising evidence highlights the necessity for structured and regular regimens of physiotherapy rehabilitation for every PD patient, a pressing need that is still unmet, due to the limited availability of physiotherapy practices (Benayoun et al., 2019) and the insufficient access to such services in remote and rural areas (Deane et al., 2002). Consequently, remote and web-based solutions for rehabilitation such as the one offered in this study can close this crucial gap and deliver this indispensable service in a capillary way.

4.2 Study Background and Rationale

4.2.1 Study Background

In France, physiotherapy is recommended by the French Health Authority (Haute Autorité de Santé [HAS]) to all PD patients to slow down the evolution of posture and motor disabilities (Haute Autorité de Santé, 2016). However, despite demonstrated benefits of rehabilitation programs in PD on gait parameters and several other aspects of life, only a fraction of PD patients are able to actually benefit from conventional physiotherapy rehabilitation sessions (Deane et al., 2002). This is due to the limited number of practices unable to meet the rising demand, as well as to their insufficient geographical coverage, de facto excluding patients residing in rural and remote areas (Benavoun et al., 2019). Recent data from the French Institute of Research and Statistics (Direction de la recherche, des études, de l'évaluation et des statistiques [DREES]) shows that up to 33% of the population in France resides in a municipality lacking a physiotherapy practice (Vergier and Chaput, 2017). Moreover, the recent COVID-19 pandemic has highlighted the fragility of the rehabilitation system for PD patients as it currently stands, with many countries discontinuing their in-person rehabilitation services during regional or national lockdowns (Bettger et al., 2020), often resulting in a total absence of physical activity (Cavallieri et al., 2021) and causing significant negative impacts on the functional abilities of PD patients (Braun et al., 2021). Telemedicine or remote rehabilitation services are therefore currently being considered to complement or as an alternative to in-person practices to overcome such limitations (Barbour et al., 2016; Vellata et al., 2021).

In this context, FeetMe Rehabilitation is an innovative technology combining connected insoles with a mobile application and a web platform to facilitate education and training on gait and mobility specifically for PD patients. Additionally, since patients can train in their home environment, FeetMe Rehabilitation ensures equal access to this essential service, overcoming constraints due to the place of residence of patients and the availability of rehabilitation centres in their area, therefore fulfilling the increasingly unmet need for physiotherapy in this patient population.

4.2.2 Study Rationale

The use of wearables and their applications to remote care could complement the conventional medical practice in PD, creating a more pervasive and capillary distribution of rehabilitative care. The FeetMe devices are expected to have their major advantage by being able to encompass areas and segments of the population that traditional care cannot efficiently reach. The FeetMe home-based rehabilitation

program with it's targeted battery of rehabilitation exercises and personalised patient follow-up service has the long-term objective of slowing down disease progression, aims at improving patient mobility and consequently reducing the risk of falls - the ultimate driver of disability for patients and of the financial burden for the health system - and at improving overall quality of life. This study has the goal to evaluate the effectiveness of the FeetMe program compared to conventional physiotherapy in participants by assessing impact on both primary motor and secondary non-motor symptoms of PD patients and quality of life.

This study has the potential of informing clinicians and physiotherapists about how new remote medicine technologies could have an impact on ameliorating the progress of their patients, particularly those that would normally not have the possibility of following a consistent, well-structured regimen of rehabilitation. Lastly, the current study findings have the potential to inform about the usefulness of novel applications as FeetMe in the clinical settings, thus further promoting the integration of digital technologies in a range of areas that support primary care and essential public health functions.

4.3 Investigational Medical Device

FeetMe® Monitor is a pair of connected insoles that measure spatio-temporal gait parameters and plantar pressure to support the mobility assessment of individuals. FeetMe® Rehabilitation is a mobile application used together with FeetMe Monitor Insoles. It has been specifically developed following the HAS recommendations for rehabilitation of PD patients. It consists of exercises which are widely used in physiotherapy practice of these patients, are clinically validated and are well described in literature (Ashburn et al., 2008; Caglar et al., 2005; Hirsch et al., 2003; Ridgel et al., 2009). It composes of static exercises for balance training and muscle strengthening and dynamic exercises to improve gait quality and endurance (Appendix A). The application allows patients to perform rehabilitation at home while receiving real-time biofeedback.

Additionally, the solution includes a web platform called the FeetMe® Mobility Dashboard that allows the healthcare professionals to remotely visualize and therefore track their patients' activity. The person in charge of the follow-up (a specialist in adapted physical activity (APA)) can adapt the rehabilitation program based on the patients' progress and compliance shown in the dashboard.

Depending on the user, the solution is not used in the same way. For Patients randomized in conventional physiotherapy group, they will use the FeetMe Evaluation application to import data stored within the insoles worn. For patients in the FeetMe arm, they will use the application FeetMe Rehabilitation to import their data and to perform exercises recommended on the program (Appendix S).

4.4 FeetMe Rehabilitation Service

Feet-Me rehabilitation is a comprehensive program that includes several components, the insoles, the application that hosts the excercises and the service by an adapted physical activity (APA) specialist who collaborates with the patient's health care team. During exercises, the phone app guides the patient using the data from the insoles. Additionally, a direct biofeedback is given to the patient after each excercise based on the insole data. The insole data is also transmitted and visualized on an internal FeetMe webportal called Dashboard. This enables the APA to review the data coming from the insoles and make objective conclusions about e.g.: excercise time, frequency and efficiency. Using this data along with the patient's reported information, the APA can make informed decisions in adapting the rehabilitation program to suit the patient's needs.

There are three training programs developed of different intensity (Program A, B and C, program A being the most intensive (Appendix B)) to which a patient can be allocated during the first three months of the FeetMe rehabilitation. The programs differ in the combination and the amount of excercises. A decision tree (Appendix B) is put in place to define which program intensity is the most suitable for a

patient to begin with. To select the appropriate program the necessary information will be collected using a standardised form. The (APA) specialist assigned to the study will validate the content during an introductory phone call with the patient. Maximal walking time without pause (> or < to 30min), need of walking aid and/or a caregiver, amount of free time to practice a physical activity, active (> 30min/day) or sedentary (<30min/day) lifestyle are the parameters to be evaluated.

For example, for patients at the onset of their disease who are able to walk more than thirty minutes without break and have at least four hours per week to practice, program A will be scheduled. On the contrary, for sedentary patients with a more advanced disease stage and therefore more compromised balance and mobility, program C will be the most adapted. During the introductory phone call the initial training will also be scheduled.

The programs have been created based on the four principles the HAS recommendations: intensity, diversity, regularity and continuity and were co-developed with neurologists who are experts of the field. The practice sessions are composed of specifically selected exercises as well as free walking. The principle is to gradually increase the rehabilitation intensity throughout the three months by more and longer practice sessions and more free walking activity. The program have longer total weekly duration every three weeks, with the exception of Program A that reaches the highest intensity level at Week 7 (5 hours per week). Sessions are composed of balance exercises (5 to 10 minutes), muscle strengthening exercises (5 to 10 minutes), gait quality training (5 to 10 minutes) and endurance exercises (15 to 30 minutes), always the same order. This overall schedule follows literature recommendations (Ashburn et al., 2008; Caglar et al., 2005; Ellis et al., 2005; McGinley et al., 2011; Ridgel et al., 2009) of intensive therapies. It also ensures that the program remains dynamic and versatile in order to maintain the motivation through. In case a patient originally assigned to the FeetMe arm decides to continue up to 6 months, the patient pursues the exercises and the level of intensity recommended in week 12.

Figure 1.	Example o	f a rehabi	litation p	program -	Program 1	В
-----------	-----------	------------	------------	-----------	-----------	---

Periods	Nb sessions	Duration of sessions	Free walking ⁄ week	Total weekly time
W1-W3	3x/week	30min	60min	=2h3o
W4-W6	4x/week	30min	60min	=3h
W7-W9	4x/week	45min	60min	=4/1
W10-W12	4x/week	60min	60min	=5h
W12-W24 (if the patient pursues)	4x/week	60min	60min	=5h

Once the patient has the devices available at their home the rehabilitation program starts with the initial remote training during which the APA specialist explains to the patient the usage of the devices, the safety instructions to follow for ensuring the security of the patient when practising and describes the program, the exercises and how to perform a walking test. Once these first steps are done, the recommended exercises are tested to check if they are well adapted and see if the safety instructions previously described are followed by the patient. During training the patient uses the application on the mobile device. Instructions are given on the screen on how the patient should move reaching a given target. After each exercise a direct biofeedback on the performance is visualised. At the end of the training a specific questionnaire is sent to evaluate the patient's satisfaction regarding the initial training (Appendix C).

Once the program has started regular follow-up calls are scheduled during which the APA specialist discusses with the patients their progress based on the data available in the Mobility Dashboard (e.g.: the patient has difficulties to start his walking with a heel strike) and the feedback of the patient. The calls are conducted in accordance with the Sponsor's internal standard operating procedure. They are initially more frequent (weekly and then bi-weekly). If a patient proceeds up to six months the calls become monthly. During the call a standard set of questions is always asked but the discussion is also adapted to the situation, focusing on motivation, resolving difficulties the patient might face, advising on the movements to be carried out and reviewing the results obtained. Each call is documented in a report and standard data are databased (e.g.: potential adverse events, reason for non-compliance, reported device deficiencies). The reports are also sent to the investigators. If it turns out that an adaptation to the rehabilitation program is needed (e.g. : the patient has difficulties to finish an exercise or/and session or it's easy for the patient to complete all sessions planed in a week) an increase or decrease in the intensity of the program will be applied to match the patient's needs (Appendix B). In addition, if the APA observes that the patient has a low success percentage on an exercise, he will guide them how to improve theresults. All modifications must be validated by the investigator before execution.

The patients' satisfaction is evaluated by the use of a questionnaire at 1, 3 (and 6 months, if applicable) (Appendix D). At the end of the program patients return the devices to the site. *Figure 2*. *Rehabilitation Program Follow up schedule*

4.5 Conventional physiotherapy

The control arm in the study consists of patients who have a prescription for conventional physiotherapy and did not get randomised into the FeetMe arm. Their rehabilitation should typically follow the HAS recommendations nevertheless, in order to make this group the most representative of real life the protocol will not standardise what is performed as part of the conventional physiotherapy. Patients who have no access to physiotherapy despite having a prescription will therefore also be part of the conventional physiotherapy arm.

The only restrictions are the ones specified in the eligibility criteria for both arms, i.e.: patients who had LSVT Big therapy within the past 12 months or are scheduled to have it during the course of the study or patients performing vigorous exercise more than 3 times a week, 30 mins or more per session either as part of their rehabilitation or otherwise, are excluded.

Patients will be asked to track their conventional physiotherapy using the weekly diary in Appendix F so the method and the time spent on rehabilitation can be evaluated and compared for analysis.

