	13.	Comfortable with the use of a smartphone. If assistance is required for the use of FeetMe technology, a caregiver or volunteer is fully available to assist the patient.
	14.	Willingness to be regularly contacted via phone-calls.
	15.	Willingness to suspend conventional physiotherapy treatment and start the FeetMe rehabilitation program, if applicable.
	16.	French speaker.
	Pat	ients must not fulfil the following criteria:
	Exe	clusion criteria
	1.	Medical history indicating a Parkinsonian syndrome other than idiopathic PD.
	2.	Unable to walk without walking aid or presence of an injury preventing the patient to walk.
	3.	Any relevant comorbidity or vestibular/visual dysfunctions limiting locomotion or balance.
	4.	Clinically significant comorbidities which in the judgement of the investigator may preclude the reliable gait assessment of the patient.
	5.	Patients with poor wound healing or broken skin on the feet.
	6.	Patients with foot implants.
	7.	Montreal Cognitive Assessment (MoCA) score $\leq 24/30$.
	8.	Patients with dementia.
	9.	Patients with apathy.

	10. Participation in another clinical trial with an investigational drug/ therapeutic within the three months before screening and during the study, unless agreed by the Sponsor.
	11. Patients who had Lee Silverman Voice Treatment (LSVT) Big therapy within the past 12 months or have it planned during the course of the study.
	12. Patients with Deep Brain Stimulation planned during the first 12 weeks of the study.
	13. Patients with pacemakers.
	14. Patients performing vigorous exercise > three times a week, 30 mins or more per session.
STUDY DESIGN AND ASSESSMENTS	This is a multicentre, controlled, randomised in two parallel-groups, open-label, study designed to evaluate the efficacy of FeetMe home- based self-rehabilitation program in comparison to conventional physiotherapy, including no physiotherapy in patients with PD. The study consists of a screening period, a primary intervention period of 12 weeks and a long-term intervention period of 12 weeks.
	Screening

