5 STUDY OBJECTIVES AND ENDPOINTS

Table 5.1 Study Objectives and Endpoints

Primary Objective	Primary Endpoints				
To evaluate the efficacy of FeetMe home-based rehabilitation program compared to conventional physiotherapy at Week 12 in PD patients assessed by gait velocity.	Change from baseline to Week 12 (Visit 3) in gait velocity (cm/s) assessed during the 6 Minutes Walk Test (6MWT).				
Key Secondary Objective	Key Secondary Endpoint				
To evaluate the efficacy of FeetMe home-based rehabilitation program compared to conventional physiotherapy at Week 12 in PD patients assessed by stance time variability.	Change from baseline to Week 12 (Visit 3) in Stance Time Variability assessed during the 6 Minutes Walk Test (6MWT).				
Secondary Objectives	Secondary Endpoints				
To evaluate the efficacy of FeetMe home-based rehabilitation program compared to conventional physiotherapy at Week 12 in PD patients assessed	• Rate of falls at Week 12 (Visit 3) based on the results of the falls diary.				
 by: rate of falls standard gait and balance exercises 	• Change from baseline to Week 12 (Visit 3) in the asymmetry of the swing duration assessed during the 6 Minutes Walk Test (6MWT).				
MDS-UPDRS Part IIIquality of life	• Change from baseline to Week 12 (Visit 3) in the MiniBESTest.				
	• Change from baseline to Week 12 (Visit 3) in MDS-UPDRS part III sub-score.				
	• Change from baseline to Week 12 (Visit 3) the results of the Parkinson Disease Questionnaire (PDQ-39)				
Exploratory Objectives	Exploratory Endpoints				

• To explore the long term efficacy home-based rehabilitation program to conventional physiotherapy in pa	of FeetMe compared atients who	Rate of falls at Week 24 based on the results of the falls diary. Change from Baseline to Week 24 (Visit 4)
continue to Week 24		and from Week 12 (Visit 3) to Week 24 in:
• To explore the maintenance of the 3 months in patients who stop phy at Week 12.	effect after vsiotherapy	- Gait velocity (cm/s) assessed during the 6MWT
 To explore the efficacy in patients of from one treatment to the other at X 	who switch Veek 12	- Stance Time Variability assessed during the 6MWT
	V CCR 12.	- Asymmetry of the swing duration assessed during 6MWT
		- the Mini-BESTest
		- MDS-UPDRS Part III sub-score
		- the results of the PDQ-39
	•	Change from Baseline to Week 12 (Visit 3) and to Week 24 (Visit 4) and from Week 12 to Week 24 in the:

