- provide the opportunity to those patients on the conventional physiotherapy arm who will not find a therapist during the study to get access to treatment by switching to FeetMe;
- assess the ratio of the willingness to continue on the FeetMe arm in comparison to the conventional arm;
- assess the maintenance of the treatment effect in patients who decide to stop;
- compare efficacy of the two treatment within the same individual who decides to switch;
- compare the long-term efficacy of the two treatments at 6 month in patients who continue on their original allocation.

Based on the emerging data, the Sponsor may decide to open an extension phase, where all participants have the option to take part or prolong their participation in the FeetMe rehabilitation program. Such extension to this study may be offered to all patients, contingent on the Sponsor's decision to implement it and could be described in a separate document.

In case study conduct will be compromised by the COVID-19 pandemic a contingency plan will be provided in a clinical investigational plan addendum.

FeetMe reserves the right to temporarily suspend or prematurely discontinue the study at any time. The study may also be terminated prematurely at any time when agreed by both the Investigators and the Sponsor as being in the best interest of the patients. In terminating the study, FeetMe and the Investigator will ensure that adequate consideration is given to the protection of the patients' interests. If the study is prematurely terminated or suspended, FeetMe will inform the Investigators/institution and the regulatory authorities and IEC in accordance with applicable regulatory requirements. In addition, arrangements will be made for the return of all study material provided by the Sponsor.

CIP Number 2023-A00150-45 Final version 0.2

CONFIDENTIAL May 2023

Figure 3. Schematic of the study design

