7.4 Primary Intervention Period

Following the Baseline Visit, all patients will begin their 12-week physiotherapy (or no-physiotherapy) regimen according to their randomisation.

During this period:

- All patients will participate in the Remote Gait Monitoring 1 and Visits 1-3 (Sections 7.3.1, 7.3.2, 7.3.3).
- Patients on the Conventional Physiotherapy arm, if they have access to it will start or continue their conventional physiotherapy and will keep track of it using the Conventional Physiotherapy Tracking Sheet (Appendix F). Patients who did not have access to CPt at the time of inclusion but manage to arrange one during the Primary Intervention Period will restart their PIP.
- On the other arm patients will start the FeetMe rehabilitation program (Section 4.4, Appendix A and B).
- In addition, all patients will keep a falls diary (Appendix G).

7.4.1 Remote Gait Monitoring 1

At the end of the Baseline Visit, all patients will take the FeetMe Insoles, mobile devices and chargers with them to their homes. A Patient User Guide will be provided.

- All patients will use the insoles remotely while performing their day-to-day activities (including physiotherapy) for two weeks. Data will be recorded in standalone mode (without a phone).
- Patients will download the data from the insoles at the end of each day.

7.4.2 Visits 1 and 2

Four and eight weeks after Baseline Visit, two remote visits (Visit 1 and 2) will take place. Patients will be asked to fill in the following questionnaires:

- PDSS-2
- Pain VAS
- Parkinson Disease Questionnaire, Short Form (PDQ-8).

7.4.3 Visit 3

Twelve weeks after Baseline Visit, that is, at the end of the 12-week Primary Intervention Period, all patients will participate in an in-clinic visit (Visit 3), where they will perform the same series of assessments as in the Baseline Visit. Patients will need to bring their FeetMe devices, their diaries, trackers and filled-in questionnaires to the visit.

The following assessments will be performed at Visit 3:

- Gait Assessments, which must be performed in the ON-phase:
 - 6 Minutes Walk Tests (6MWT)
 - Mini-BESTest.

During the 6MWT and the Mini-BESTest patients must wear the insoles. Specific instructions set out in the Site User Manual must be followed when setting up and executing the assessments.

- Disease specific rating scales:
 - MDS-UPDRS
- Other Assessments:
 - FOG-Q
 - PDSS2
 - Pain VAS
 - PDQ39

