9.2.1 Estimands for primary and key secondary objectives

The main treatment policy estimands for the primary and key secondary objectives of this study, are defined in Table 9.2 below. This table describes the four attributes of target population, endpoint, strategy for addressing intercurrent events, and population-level summary for the endpoints (ICH E9 (R1)).

Target population	Endpoint	Strategy for addressing intercurrent events	Population-level summary				
Primary object	Primary objective in line with H0_1_Primary						
Idiopathic Parkinson'sChange baselinefrom to 		All available data to be included. This is in alignment with the FAS definition. If a patient has a fall up to week 12 and has available week 12 gait data, then the week 12 data will be used and the fall ignored. If the week 12 measurement is not available, whatever the reason (death or injury) the baseline data are used (the patient is not excluded).	In Idiopathic PD patients on CPt, what is the change in gait velocity 12 weeks after randomisation, assessed during the 6MWT, between Conventional Physiotherapy and FeetMe Rehabilitation and whilst the patient is on treatment?				
Key secondary	objective in line w	ith H0_2_KeySecondary					
Idiopathic Parkinson's Disease (PD) patients on Conventional Physiotherapy (CPt)	Change from baseline to Week 12 in stance time variability (ms) assessed during the 6MWT.	All available data to be included. This is in alignment with the FAS definition. If a patient has a fall up to week 12 and has available week 12 gait data, then the week 12 data will be used and the fall ignored. If the week 12 measurement is not available, whatever the reason (death or injury) the baseline data are used (the patient is not excluded).	In Idiopathic PD patients on CPt what is the change in stance time variability 12 weeks after randomisation, assessed during the 6MWT, between Conventional Physiotherapy and FeetMe Rehabilitation and whilst the patient is on treatment?				

Table 9.2 Treatment policy estimands for the primary and key secondary objectives

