9.2.2 Overall testing strategy

In line with the primary and key secondary objectives of the statistical analysis (see Table 9.2), a confirmatory hierarchical testing procedure will be applied. As a first step, the null hypothesis 'H0_1_Primary' will be tested at the 2-sided alpha level of 0.05. If this null hypothesis is rejected, the key secondary endpoint hypothesis 'H0_2_KeySecondary' will then be tested in a second step, again using a 2-sided alpha of 0.05.

H0_1 Primary: The null hypothesis to be tested for the primary endpoint is that the change in week 12 gait velocity from baseline in FeetMe Rehabilitation arm is equal to that in the conventional physiotherapy arm. The alternative is that they are not equal. Superiority will be declared if the difference (FeetMe Rehabilitation vs Conventional Physiotherapy) is significantly greater than 0 at the two-sided type I error level alpha=0.05.

H0_2 KeySecondary: The null hypothesis to be tested for the key secondary endpoint is that the change in week 12 stance time variability from baseline in FeetMe Rehabilitation arm is equal to that in the conventional physiotherapy arm. The alternative is that they are not equal. Superiority will be declared if the difference (FeetMe Rehabilitation vs Conventional Physiotherapy) is significantly greater than 0 at the two-sided type I error level alpha=0.05.

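### The estimand targets patients on conventional physiotherapy and the superiority rule names only physiotherapy, but the control arm deliberately includes patients receiving none

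*Protocol*

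**What the plan says.** **Content of the control arm.** Four places in the protocol show that untreated controls are intended:

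- Section 4.5: "Patients who have no access to physiotherapy despite having a prescription will therefore also be part of the conventional physiotherapy arm". The same section leaves the content of physiotherapy unstandardised so that the arm reflects real life.
- Synopsis, study design: the comparator is "conventional physiotherapy, including no physiotherapy in patients with PD".
- Section 7.4: patients begin a "12-week physiotherapy (or no-physiotherapy) regimen according to their randomisation".
- Section 6.1: one purpose of the switch option at Week 12 is to "provide the opportunity to those patients on the conventional physiotherapy arm who will not find a therapist during the study" access to treatment.

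Inclusion criterion 8 (section 6.3.2) requires a prescription for physiotherapy, not its receipt.

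**Confirmatory wording.**

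- Primary objective (synopsis and Table 5.1): "To evaluate the efficacy of FeetMe home-based rehabilitation program compared to conventional physiotherapy at Week 12 in PD patients assessed by gait velocity".
- Table 9.2 gives the target population as patients on conventional physiotherapy and asks: "In Idiopathic PD patients on CPt, what is the change in gait velocity 12 weeks after randomisation".
- Section 9.2.2: "Superiority will be declared if the difference (FeetMe Rehabilitation vs Conventional Physiotherapy) is significantly greater than 0".
- Section 9.5.1: the primary analysis is one time-by-arm contrast, adjusted for prior rehabilitation status with centre as a random effect.

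**The concern.** A patient with a prescription and no therapist is eligible and can be randomised. With a baseline gait measurement, that patient is in the full analysis set. The same patient is outside the target population of Table 9.2, so the estimand describes a narrower population than the trial enrols.

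The second problem is the conclusion. The pooled contrast averages two effects: FeetMe against physiotherapy, and FeetMe against nothing. Adjusting for prior rehabilitation status improves balance and precision but does not separate them. If FeetMe were no better than physiotherapy but better than no treatment, the test could still be positive, and section 9.2.2 would then declare superiority over conventional physiotherapy. Payers and clinicians would act differently on *better than physiotherapy* and on *better than what patients can currently obtain*.

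**Working it through.** **1. The plan's own figure.** Section 9.4 gives a difference of 14 cm/s, an SD of change of 27 cm/s, two-sided alpha 0.05 and 80% power. With correlation 0.5 the SD of change is 27 × √(2 × (1 − 0.5)) = 27, as stated. The noncentral t gives power 0.798 at 59 per group and 0.804 at 60, so 60 reproduces. Allowing for 20% dropout, 60 / 0.8 = 75 per group. There is no arithmetic error.

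**2. What the pooled contrast estimates.** Let p be the share of controls without physiotherapy, D the effect against no treatment, and E the effect against physiotherapy. Then

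pooled effect = (1 − p) × E + p × D.

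With E = 0 this is p × D. The protocol gives neither p nor D, so both are assumptions. For D, I take the small, moderate and large differences quoted in section 9.4 (6, 14 and 22 cm/s). The 33% in section 4.2.1 ("up to 33% of the population in France resides in a municipality lacking a physiotherapy practice") concerns the general population and serves only as one point in the range for p.

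**3. Chance of a significant positive result when E = 0.** With 60 per arm and SD 27, the standard error is 27 × √(2/60) = 4.93 cm/s, the critical t on 118 degrees of freedom is 1.98, and the smallest significant observed difference is 1.98 × 4.93 ≈ 9.8 cm/s. The noncentrality is p × D / 4.93. The second SD, 27 × √(1 − 0.5²) = 23.4, approximates the baseline adjustment in the cLDA model; its standard error is 4.27.

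| D (cm/s) | p | p × D (cm/s) | SD 27 | SD 23.4 |
|---|---|---|---|---|
| any | 0 | 0 | 2.5% | 2.5% |
| 6 | 50% | 3.0 | 9% | 10% |
| 14 | 20% | 2.8 | 8% | 10% |
| 14 | 33% | 4.6 | 15% | 19% |
| 14 | 50% | 7.0 | 29% | 37% |
| 22 | 50% | 11.0 | 60% | 72% |

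The calculation assumes a common SD in treated and untreated controls and a two-sample t-test in place of the full model.

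**4. Precision within a stratum.** Assume an even split, so 30 evaluable patients per arm in each stratum. The 95% half-width is 2.00 × 27 × √(2/30) ≈ 14 cm/s, or 2.00 × 23.4 × √(2/30) ≈ 12 cm/s. An interval of ±12 to 14 cm/s is about as wide on each side as the 14 cm/s the trial is designed to detect.

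**The case against.** The best defence is that *conventional physiotherapy arm* is a defined term. Section 4.5 says who is in it and why, and the synopsis, section 6.1 and section 7.4 repeat it. Section 9.2.2 compares randomised arms, which is accurate under that definition. Much of this stands: the comparator is open, pragmatic and legitimate, and of the objective, hypotheses and Table 9.2 only the last describes the patients themselves as on physiotherapy. What does not stand is that disclosure in the design sections repairs the estimand table and superiority rule, which govern the claim and carry no such qualification.

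The protocol also contains a mitigation. Under section 7.4, controls without access at inclusion who arrange physiotherapy during the primary period restart that period. This may lower p, but it does nothing for those who never find a therapist, whom section 6.1 expects.

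Three stronger readings are tempting and not supported:

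- *The trial's type I error is inflated.* It is not. The test of equality between the randomised arms keeps its level. The percentages above describe how often a true difference between arms would be read as superiority over physiotherapy.
- *A third or more of controls will be untreated.* The protocol gives no such share. The 33% refers to where people in France live, not to prescribed patients recruited at six centres.
- *The missing stratum analysis is an omission.* Section 9 refers full details to the statistical analysis plan, which is not at hand. Nor could such an analysis settle a claim against physiotherapy: prior rehabilitation is a baseline status, section 7.4 lets controls with access start physiotherapy after randomisation, and section 8.4 counts aerobic exercise as rehabilitation.

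**Conclusion.** The concern holds as a mismatch between the confirmatory wording and the arm that will be tested. Table 9.2 names a population narrower than the one enrolled. The objective and superiority rule name a comparator that only part of the control arm is certain to receive. A positive pooled test would support superiority over usual care with incomplete access; by itself it would not support superiority over physiotherapy.

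This conclusion needs only p above zero, which sections 4.5 and 6.1 expect. Its size does depend on assumptions. With no benefit over physiotherapy, the chance of declaring superiority runs from about 8% (SD 27, 14 cm/s over none, 20% untreated) to 29% with 50% untreated, or 10% to 37% at SD 23.4. Other pairs of p and D move it further in either direction, so no single figure should be quoted as the expected risk.

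**What to change.** 1. In the primary and key secondary objectives, both null hypotheses in section 9.2.2 and Table 9.2, name the comparator as *usual care (conventional physiotherapy where accessible, otherwise none)*.
2. In Table 9.2, replace the target population with *PD patients with a prescription for physiotherapy*, in line with inclusion criterion 8.
3. Word the superiority conclusion in section 9.2.2 to match.
4. As a supportive, non-confirmatory analysis, report the arm-by-time effect within each stratum of prior rehabilitation status, which is already a minimisation factor. Say that this status is an imperfect proxy for physiotherapy received over the 12 weeks and that the intervals will be wide. It should not be the sole basis for a claim against physiotherapy.

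The comparator, enrolment, sample size and alpha do not change. The cost is a narrower headline claim and one extra model term.
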